8.1 Sequence of Analyses

The final analysis will be performed at the end of the trial, 12 months after the last subject's first dose of tepotinib. The final analysis will occur once all trial data is in-house, all data queries are resolved, and the database is fully locked.

9 Changes to the Planned Analyses in the Clinical Trial Protocol

The following are changes to the planned analyses in the clinical trial protocol:

- Physical examination results at baseline will not be presented since these are not collected on the eCRF. Relevant findings had to be entered on the medical history or adverse event eCRF page.
- Relative dose intensity will be summarized rather than treatment compliance.
- The Pd Analysis Set is not defined in this SAP since all Pd related analyses will be carried out on the intent-to-treat (ITT)/safety (SAF) analysis set.
- The deterioration of symptoms assessed by FHSI-8 is defined in accordance with the scoring guidance in appendix 2 as at least a 4-point decrease compared with the baseline value.
- Summaries of sum of longest diameter (SOLD) data are included but these are not explicitly mentioned in the protocol.
- Summaries of quality of life data are included but these are not explicitly mentioned in the protocol.
- Duration of response will be calculated and presented in data listings but this is not explicitly mentioned in the protocol.
- The underlying disease or medical condition related to etiology subgroups will be hepatitis C virus (HCV), and other as opposed to hepatitis B virus (HBV) and other as defined in the protocol.

• 60

• A decrease in AFP level of more than 20% at the Cycle 3 assessment, or the last assessment for subjects that terminated treatment prior to the Cycle 3 assessment, as compared with baseline.

Otherwise, the statistical methods as described in the protocol will be adopted.

10 Protocol Deviations and Analysis Sets

10.1 Definition of Protocol Deviations and Analysis Sets

Important protocol deviations are protocol deviations that might significantly affect the completeness, accuracy, and/or reliability of the study data or that might significantly affect a subject's rights, safety, or well-being.

Important protocol deviations include:

- Subjects that are dosed on the study despite not satisfying the inclusion criteria;
- Subjects that develop withdrawal criteria whilst on the study but are not withdrawn;
- Subjects that receive the wrong treatment or an incorrect dose;
- Subjects that receive an excluded concomitant medication;
- Deviation from good clinical practice.

The following deviations will be identified and confirmed prior to or at the Data Review Meeting at the latest.

- Deviations from the inclusion and exclusion criteria
- Deviations post inclusion

Important protocol deviations will be determined for all subjects by either site monitoring, medical review processes or programming based on the inclusion/exclusion criteria or other criteria presented in the protocol.

All important protocol deviations will be documented in CDISC datasets whether identified through site monitoring, medical review or programming. Important protocol deviations to be identified are specified in Appendix 1 and will be presented in a summary table and data listing.

10.2 Definition of Analysis Sets and Subgroups

Screening Analysis Set

The Screening Analysis Set includes all subjects who signed the Informed Consent Form (ICF). The Screening Analysis Set will be used for the display of disposition data. Rescreened subjects will be counted once in the Screening Analysis Set. For subjects who are rescreened, the most recent data will be presented in listings.

Intent-to-Treat/Safety Analysis Set

The ITT/SAF Analysis Set includes all subjects who have been administered at least one dose of tepotinib. The ITT/SAF Analysis Set will be used for all safety and efficacy analyses.

₹\//

The below subgroup analyses may be performed on the primary endpoint and some secondary endpoints. The subgroup analyses are exploratory in nature. The following subgroups will be defined:

- Age: < 65 years versus ≥ 65 years
- Gender: male versus female
- Country
- Baseline ECOG: 0 versus 1
- Vascular invasion and/or extrahepatic spread: presence versus absence
- Underlying disease or medical condition related to etiology: HCV versus other
- AFP elevation at baseline: ≥ 200 IU/mL versus < 200 IU/mL
- Prior local-regional therapy: yes versus no
- Baseline c-Met Status: Immunohistochemistry (IHC): IHC 0, IHC 1+, IHC 2+, IHC3+
- Baseline c-Met Status: In Situ Hybridization (ISH): ISH+, ISH-
- Baseline Cancer-Associated Fibroblast (CAF) HGF: above the median, below/at the median, not done, not evaluable.
- Baseline Cytoplasmic HGF: above the median, below/at the median, not done, not evaluable
- Baseline Circulating HGF
 - o Above the median, below/at the median, not done, not evaluable
 - Above upper quartile (25% quantile), below/at upper quartile, not done, not evaluable
- Baseline Shedded c-Met
 - O Above the median, below/at the median, not done, not evaluable
 - o Above upper quartile, below/at upper quartile, not done, not evaluable
- Baseline IL-8
 - O Above the median, below/at the median, not done, not evaluable
 - Above upper quartile, below/at upper quartile, not done, not evaluable
- Baseline c-Met Amplification (ISH): c-Met amplification +, c-Met amplification –
- Baseline HCV Status: HCV versus non-HCV
- Baseline HBV Status: HBV versus non-HBV

Baseline HBV/HCV Status: HBV or HCV versus neither HBV nor HCV

Analyses	Screening Analysis Set	ITT/SAF Analysis Set	
Disposition	✓		
Demographics		✓	
Baseline Assessments		✓	
Past and Concomitant Therapies		✓	
Compliance and Exposure		✓	
Primary		✓	
Secondary		✓	
CCI			
CCI			
CCI			
Safety and Tolerability		✓	

11 General Specifications for Statistical Analyses

All analyses (production of tables, listings and figures) will be performed using SAS® Software version 9.2 or higher (Statistical Analysis System, SAS-Institute, Cary NC, USA).

Last date known to be alive:

The following dates will be used to determine the last date known to be alive prior to or at data cut-off:

- All subject assessment dates (laboratory blood draws, vital signs, performance status, ECG, tumor assessments, quality of life assessments)
- Start and end dates of anti-cancer therapies administered after study treatment discontinuation.
- Adverse Event (AE) start and end dates
- Last known alive date collected on the 'Subject Status/Survival Follow-up' eCRF (do not use date of survival follow-up assessment unless status is 'alive')
- Study drug start and end dates

Unscheduled visits:

Data collected at unscheduled visits will not be included in by-visit summaries of data but may contribute to baseline value derivations and analyses in which post-baseline data is considered (e.g. best/worst on-treatment value).

End of Treatment visits:

End of Treatment visits will be included as a separate time point in by-visit summaries of data and may also contribute to analyses in which post-baseline data is considered (e.g. best/worst on-treatment value).

Significance level:

The significance level is 5% one-sided. The primary efficacy endpoint analysis is described in Section 16.1. Confidence intervals (CIs) will be two-sided with a confidence probability of 90%, unless otherwise specified.

Presentation of continuous and qualitative variables:

Continuous variables other than will be summarized using descriptive statistics if not otherwise specified, i.e.

- number of subjects (N), number of subjects with non-missing values
- mean, standard deviation
- median, first quartile (Q1) third quartile (Q3)
- minimum and maximum

Pharmacokinetic data (concentrations) will be summarized using N, arithmetic mean, standard deviation, median, minimum, maximum, and coefficient of variation (CV) (%).

Qualitative variables will be summarized by counts and percentages, with percentages based on the number of subjects in the analysis set of interest, unless otherwise specified. Counts of missing observations will be included in the denominator and presented as a separate category in shift from baseline summaries. In general, percentages will be reported to 1 decimal place unless greater precision is deemed appropriate.

By-visit displays:

By-visit summaries will include all planned visits until the last visit with at least 3 ongoing subjects.

Definition of baseline:

In general, the last measurement prior to first administration of trial treatment will serve as the baseline measurement. For ECG parameters, the average of up to three measurements at the last visit prior to the first administration of trial treatment will serve as the baseline measurement.

Definition of duration:

Duration will be calculated as the difference of start and stop date + 1 (e.g. survival time (days) = date of death – date of first trial treatment administration + 1), if not otherwise specified.

The time since an event (e.g. time since first diagnosis) will be calculated as the reference date minus the date of the event.

Conversion factors:

The following conversion factors will be used to convert days into months or years:

- 1 month = 30.4375 days
- 1 year = 365.25 days.

Definition of treatment day:

Treatment day is defined relative to the start date of trial treatment. Treatment day 1 is the date of first administration of trial treatment, and the day before is defined as Treatment day -1 (no Treatment day 0 is defined).

Definition of on-treatment period:

The on-treatment period is defined as the time from the first trial treatment administration to the last trial treatment administration date + 33 days.

Definition of completion of a cycle:

A cycle is considered complete if the treatment end date minus the treatment start date plus one is greater than or equal to the following:

Cycle 1 (week 1 – 3)	21
Cycle 2 (week 4 – 6)	42
Cycle 3 (week 7 – 9)	63
Cycle 4 (week 10 – 12)	84
	•••
Cycle x (week $(x-1)*3+1-x*3$)	x*21

Handling of missing data:

Unless otherwise specified in this SAP, all data will be evaluated as reported and no imputation of missing values will be done. In subject data listings, imputed values will be presented (if applicable), and the imputed information will be flagged.

Missing statistics (i.e. when they cannot be calculated) will be presented as "nd" (i.e. not done). For example, if n=1, the measure of variability (standard deviation) cannot be computed and will be presented as "nd".

Partial dates are allowed for some of the date fields as collected on the eCRF. Partial dates will not be imputed unless they are required for assignment of a medication to previous or concomitant or an adverse event to treatment emergent. The date imputation rules for adverse events are described in Section 17.1.

12 Trial Subjects

The subsections in this section include specifications for reporting subject disposition and treatment/trial discontinuations. Additionally, procedures for reporting protocol deviations are provided.

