Under the assumption of no treatment effect, the rate of MET+ subjects without progression at 12 weeks was assumed to be ~15% based on historical data. It is expected that tepotinib treatment will lead to 30% MET+ subjects without progression at 12 weeks. The null hypothesis that the true rate of subjects without progression at 12 weeks is \leq 15% will be tested using a one-stage design based on the exact binomial distribution. With a type I error rate of 5% (one-sided) if the true rate of subjects without progression at 12 weeks is \leq 15%, to reach a power of 80% if the true rate of subjects without progression at 12 weeks is 30%, this design requires 48 subjects to be treated in Phase II.

Randomization is not applicable.

8 Overview of Planned Analyses

This SAP covers the analyses for efficacy and safety for the final analysis. Statistical analyses will be performed using cleaned electronic Case Report Form (eCRF) data. An administrative interim efficacy analysis, described in a separate analysis plan, was previously performed. Further administrative interim analyses at time points that are not specified in the protocol may be performed for internal planning purposes.

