16.3 Analysis on Subgroups

Subgroups for analysis are defined in Section 10. The analysis of the primary endpoint (number of progression free subjects at week 12) and PFS and OS will be presented by subgroups.

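### Phase II SAP 10.2 labels the second circulating-HGF cut as both the upper quartile and the 25% quantile; these are different cut points, and the percentage should read 75%

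*SAP*

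**What the plan says.** Phase II SAP Section 10.2 lists the subgroups. For three baseline markers (circulating HGF, shedded c-Met and IL-8) it gives two splits each, one at the median and one at the upper quartile.

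- Circulating HGF, second split: "Above upper quartile (25% quantile), below/at upper quartile, not done, not evaluable".
- Shedded c-Met and IL-8, second split: "Above upper quartile, below/at upper quartile, not done, not evaluable", with no percentage.

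Section 11 of the same SAP, on presentation of continuous variables, uses the ordinary convention: Q1 is the first quartile and Q3 the third.

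On use, Section 16.3 states: "The analysis of the primary endpoint (number of progression free subjects at week 12) and PFS and OS will be presented by subgroups". Sections 16.1, 16.2.1 and 16.2.4 repeat this for the individual endpoints. On status, Section 10.2 says: "The subgroup analyses are exploratory in nature".

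**The concern.** A subgroup definition has to lead any two programmers to the same cut. This one does not, because the words and the number in a single line point to opposite ends of the distribution. The number is also the only numeric instruction attached to any of the three upper-quartile splits, so a programmer or validator looking for a figure to code has just this one.

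If 25% were coded, the group labelled as above the upper quartile would hold roughly the top three quarters of values instead of the top quarter. A top-quartile split is there to isolate subjects with high values. Adding the middle half of the distribution to that group would blur the contrast, and the HGF result could not be set beside the corresponding shedded c-Met and IL-8 results. The rationale in Protocol Section 3.4 separates high from moderate or low HGF/c-Met, although that text concerns tumor explants and not circulating HGF.

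There is also a question of timing. If the ambiguity is settled only after the subgroup results are known, a choice between two written cut points can look data-driven.

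**Working it through.** **Inputs**

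- Phase II size: Section 7 of the Phase II SAP says "this design requires 48 subjects to be treated in Phase II". This is the upper limit on the number with a circulating-HGF value.
- Design rates: the null rate "was assumed to be ~15% based on historical data"; the expected rate on treatment is 30%. One-sided alpha is 5% and power 80% (same section). The rule is 12 or more progression-free subjects (Protocol Section 8.5.2).
- Number with an evaluable baseline circulating-HGF value: not stated. I assume a range of 30 to 48.

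**Step 1. Reproduce the base figure.** The disputed line contains no computed figure, so the figure to check is the 48. By the exact binomial:

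- P(X ≥ 12 | n = 48, p = 0.15) = 0.0478, which is below 0.05.
- P(X ≥ 12 | n = 48, p = 0.30) = 0.8186, which is above 0.80.
- With a rule of 11 or more, the first probability is 0.0956, so 12 is the smallest admissible count.
- Searching upward from n = 30, 48 is the first size that meets both limits.

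The plan's figure reproduces.

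**Step 2. Count the groups under each cut.** Let n be the number of evaluable subjects, without ties.

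- Cut at the 75% quantile: about 0.25n above. With n = 48, 0.25 × 48 = 12 above and 48 − 12 = 36 at or below.
- Cut at the 25% quantile: about 0.75n above. With n = 48, 0.75 × 48 = 36 above and 48 − 36 = 12 at or below.
- Subjects classified differently are those between the two cuts: 36 − 12 = 24, and 24/48 = 50%.

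**Step 3. Vary the evaluable number.** Counts from untied simulated values under two quantile definitions (linear interpolation, and the averaged inverted distribution function). One entry means that both definitions agree.

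| Evaluable n | Above 75% quantile | Above 25% quantile | Classified differently |
|---|---|---|---|
| 48 | 12 | 36 | 24 (50%) |
| 47 | 12 or 11 | 35 | 23 (49%) or 24 (51%) |
| 45 | 11 | 33 | 22 (49%) |
| 44 | 11 | 33 | 22 (50%) |
| 40 | 10 | 30 | 20 (50%) |
| 36 | 9 | 27 | 18 (50%) |
| 30 | 8 or 7 | 22 | 14 (47%) or 15 (50%) |

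The share stays between 47% and 51%. About half is therefore a stable description, while the count of 24 requires all 48 to be evaluable.

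**Step 4. Which part of the line is wrong?** The disputed line uses upper quartile twice, once for each side of the cut. The two sibling markers use the same term with no percentage. The SAP's own Q1/Q3 convention makes the upper quartile the 75% quantile. Only the parenthesis disagrees.

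**The case against.** The strongest reply is that the text itself moves nobody. The line says upper quartile twice, the comparison group carries no percentage, and both sibling lines agree with the words. A careful programmer would probably cut at the 75% quantile. The parenthesis may simply be loose shorthand for the top 25% of values. This stands: the line contradicts itself and does not clearly specify the first quartile. A reader might infer that the SAP prescribes the lower quartile and so places half the trial in the wrong group. The documents do not support that. The different grouping arises only if the number is followed over the words, and it applies only to subjects with an evaluable value, because the SAP gives not done and not evaluable their own categories.

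A second reply is that the consequence is small. That also stands. The subgroups are labelled exploratory, and the visible text attaches no decision to this one. Section 10.2 says only that subgroup analyses may be done, but Section 16.3 commits to presenting them, so the output is planned.

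A third reply is that specifications for circulating markers may sit in text that is not visible: the section numbering in the available SAP runs from 13.5 to 13.7. That is possible, and I do not claim that nothing else in the SAP defines the cut. It would not make the line in Section 10.2 consistent.

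**Conclusion.** The inconsistency is real and minor. It concerns one cut point for one marker. If the parenthetical number were followed, about half of the subjects with an evaluable baseline circulating-HGF value would be classified differently from the apparent intent. That is 24 subjects if all 48 are evaluable and there are no ties, and 47% to 51% over an assumed 30 to 48 evaluable. Reading the 75% quantile as the intent rests on the wording of the line itself, the two parallel lines and the SAP's quartile convention.

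Two wider conclusions would go too far. A reader might infer that the primary result is at risk; it is not, since the test against 15%, its alpha, power, sample size and decision rule do not use this subgroup. A reader might also infer that HGF cannot be compared with the other biomarkers at all. The median splits of the three markers are defined alike and remain comparable; only the second split would differ, and only if the number were coded.

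**What to change.** In Phase II SAP Section 10.2, replace the parenthesis in the circulating-HGF line with 75% quantile, Q3. Apply the same definition to circulating HGF, shedded c-Met and IL-8, and state that the quantile is computed among subjects with an evaluable baseline value of the marker concerned.

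The cost is one number and one clarifying sentence. No data collection, sample size or primary analysis changes. The correction should be made before the subgroup outputs are produced, so that the cut cannot appear to have been chosen from the results.

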12.1 Disposition of Subjects and Discontinuations

Analysis Set: Screening

Subjects will remain in the study until death, withdrawal of consent, or trial completion. Subjects are free to withdraw from the study at any time without giving their reason(s).

The following will be summarized for all screened subjects:

- Number of subjects screened (rescreened subjects will be counted once)
- Number of subjects rescreened
- Number of subjects who discontinued from the trial prior to treatment (overall and grouped by primary reason for discontinuation)
- Number and percentage of treated subjects. (i.e. those with at least one dose of trial treatment)
- Number and percentage of subjects who completed treatment (i.e. experienced death or disease progression)
- Number and percentage of subjects who discontinued treatment (overall and grouped by primary reason for discontinuation)
- Number and percentage of subjects who discontinued study procedures (overall and grouped by primary reason for discontinuation)
- Number and percentage of subjects who discontinued survival follow-up (overall and grouped by primary reason for discontinuation)

Percentages for the summaries above will be based on the ITT/SAF Analysis Set.

Number of subjects in the Screening Analysis Set along with number and percentage of subjects in the ITT/SAF and [SCI] Analysis Sets will be presented in a separate standalone summary.

The number and percentage of subjects from each region, country and clinical site will be summarized for the screening, ITT/SAF, and Analysis Sets.

12.2 Protocol Deviations

12.2.1 Important Protocol Deviations

Analysis Set: ITT/SAF

The following summary table and listing of important protocol deviations will be provided:

- Frequency table per reason of important protocol deviations
- Listing of important protocol deviations

12.2.2 Reasons Leading to the Exclusion from an Analysis Set

This section does not apply to this trial as there is no per protocol Analysis Set defined for this study.

13 Demographics and Other Baseline Characteristics

Analysis Set: ITT/SAF

If not stated otherwise, summaries will be presented for the ITT/SAF Analysis Set. Baseline characteristics with respect to vital signs, ECG results, and hematology/biochemistry will be part of Section 17 (Safety Evaluation).

13.1 Demographics

Demographic characteristics will be summarized using the following information.

- Demographic characteristics
 - Sex:
 - o Male
 - o Female
 - Race:
 - White
 - o Black or African American
 - o Asian

- o Other
- Unknown
- Age (years): summary statistics
- Age categories:
 - 0 < 65
 - 0 65 < 75
 - 0 75 < 85
 - $\circ \geq 85$
- Country of site
 - o Belgium
 - o France
 - o Germany
 - o Italy
 - o Spain
 - Switzerland
 - United States of America

Specifications for computation:

- Age [years]:
 - o (date of given informed consent date of birth + 1) / 365.25
 - o In case of missing day only: For the derivation only, the day of informed consent and the day of birth will be set to 1 and the formula above will be used.
 - o In case of missing day and month: For the derivation only, the day and the month of informed consent and the day and month of birth will be set to 1 and the formula above will be used.

The integer part of the calculated age will be used for reporting purposes.

Site codes will be used for the determination of the subject's country of site.

A listing of demographics will be provided with all data (as collected on the "Demographics" eCRF page) and derived variables used in the above summary table.

13.2 Medical History

Medical history will be summarized as the numbers and percentages of subjects by Medical Dictionary for Regulatory Activities (MedDRA) preferred term (PT) as event category and MedDRA primary system organ class (SOC) as summary category. PT and SOC will be determined using the latest version of MedDRA. A subject will be counted only once within a given SOC and within a given PT, even if he/she had the same medical history event at different times. The data will be displayed in terms of frequency tables ordered by primary SOC and PT in

alphabetical order. Medical history data will come from the "Medical History Details" eCRF page, and a listing including all relevant medical history data will be provided.

